13.4.2 Pharmacodynamics from CSF Samples

A listing of all FAM19A5 concentrations in CSF will be presented.

13.5 Immunogenicity

The following will be assessed:

- Serum ADA
- NAbs

Incidence of ADAs and Nabs will be assessed. NAbs will be analyzed only for subjects with ADA positive results.

Immunogenicity results (the number of subjects with positive screening assay, confirmatory assay and titer assay) will be summarized by frequency tabulations. These results will be summarized by time point and dose level, which will include separate tables, and graphical frequency displays. The main PK parameters will be summarized by dose level and category of ADA status (at least one positive/negative).

Boxplots will present PK levels for each dose level by ADA status.

The details of the immunogenicity analysis will be outlined in greater detail in the SAP.

13.6 Statistical Analyses

Individual and mean serum or plasma concentration versus time curves will be presented for both linear and semi-log scales for NS101 and FAM19A5. Descriptive statistics (arithmetic and

geometric means, SD, CV%, Min, Max, and median) of the serum or plasma concentrations versus time will be presented as well for the PK and PD parameters.

Interim PK analyses will be performed for each cohort. Summary statistics will be used to describe the PK profile for this cohort. Dose proportionality may be assessed within different dose ranges if deemed appropriate with at least three doses using the power model approach. Dose-response relationship may be performed using Logistic Regression plots to assess the relationship between PK data after single dose administrations and specific AEs, when data permitting.

Summary statistics will be used to describe the PK profile for each cohort. After data base lock, the power model approach will be performed on the ln-transformed PK parameters AUC_{0-24} , AUC_{0-inf} , AUC_{0-inf} , and C_{max} , and data to investigate dose-proportionality. Non-parametric analysis will also be performed on the untransformed T_{max} data.

14. Regulatory Considerations and Quality Assurance

14.1 Institutional Review Board Approval of Protocol and Other Study Documents

The Investigator(s) agree to provide the IRB with all appropriate documents, including a copy of the protocol/amendments, ICFs, advertising text (if any), Investigator's Brochure (if any) and any other written information provided to study subjects. The trial will not begin until the Investigators have obtained the IRB favourable written approvals for the above-mentioned study documents. A properly executed written ICF shall be read, signed, and dated by each subject prior to entering the trial or prior to performing any study procedure. The original signed and dated ICF will be kept at Syneos Health and a copy will be given to the subject.

In the event that the protocol is amended, the revised protocol must be approved by the IRB prior to its implementation, unless the changes involve only logistical or administrative aspects of the trial. If a revised ICF is introduced during the study, each subject's further consent must be obtained. The new version of the ICF must be approved by the IRB, prior to subsequently obtaining each subject's consent.

The Investigator and the Sponsor's representative must sign the protocol and its amendments (if any) before initiating the study.

It is the Sponsor's responsibility to submit the protocol and its amendments (if any), and the ICFs to regulatory authorities when necessary.

14.2 Compliance

This study will be conducted in compliance with the protocol, GCP, and all applicable regulations, including the Federal Food, Drug and Cosmetic Act, U.S. applicable Code of Federal Regulations (title 21), and any IRB requirements relative to clinical studies. The study will also be conducted in compliance with the recommendations laid down in the most recent version of the Declaration of Helsinki, with the exception that registration of such Phase 1 trials in a publicly accessible database is not mandatory. As required by the Canadian regulatory agency, a Clinical Trial

Application (CTA) will be submitted before the beginning of the study and a No Objection Letter (NOL) must be received prior to dosing.

14.3 Quality Assurance Program

Syneos Health has established Quality Control (QC) and Quality Assurance (QA) systems with written SOPs to ensure that the study will be conducted and data will be generated, recorded, and reported in compliance with the protocol, GCP, and applicable regulatory requirements. A rigorous QC program is applied to ensure accuracy of all data and reports. QA oversees a complementary risk-based program of audits to assure compliance with applicable regulations and Syneos Health's prescriptive documentation.

CTCAE	Common Terminology Criteria for Adverse Events
CV	coefficient of variation
ECG	electrocardiogram
eCRF	electronic case report form
E _{max}	maximal observed effect
FIH	first-in-human
ICH	International Conference on Harmonization of Technical Requirements for Registration of Pharmaceuticals for Human Use
IV	intravenous
K _{el}	elimination rate constant
LLOQ	lower limit of quantification
max	maximum
MedDRA®	Medical Dictionary for Regulatory Activities
min	minimum
n	number of observations
NAb	neutralizing antibody
OLS	ordinary least squares
PD	Pharmacodynamic(s)

This document is confidential.

Abbreviation	Description
PK	pharmacokinetic(s)
PT	preferred term
RTF	rich text format
SAD	single ascending dose
SAE	serious adverse event
SAP	statistical analysis plan
SD	standard deviation
SOC	system organ class
SOP	standard operating procedure
SRC	Safety Review Committee
S-STS	Sheehan Suicidality Tracking Scale
T _{1/2 el}	terminal elimination half-life
TEAE	treatment-emergent adverse event
TE _{max}	time of maximal observed effect
TLFs	tables, listings, and figures
T _{max}	time to reach the maximum observed post-dose concentration
V _z	apparent volume of distribution
WHOD	World Health Organization Drug Global Dictionary

This document is confidential.

1. Purpose

The purpose of this statistical analysis plan (SAP) is to ensure that the data listings, summary tables, and figures which will be produced, and the statistical methodologies that will be used, are complete and appropriate to allow valid conclusions regarding the study objectives. Safety, tolerability, pharmacokinetic (PK), immunogenicity and pharmacodynamics (PD) analyses will all be described.

This SAP is based on the following documents:

- Protocol No. NS101_P1_01 Amendment III, dated 06-Apr-2022
- Electronic Case Report Form (eCRF) version 3.00, dated 17-May-2022
- Protocol Administrative Letter for Early Phase Studies dated 19-May-2022
- NS101_P1_01_Electronic CRF Completion Guidelines_Final 3.0

The plan may change due to unforeseen circumstances; any changes made after the plan has been finalized, will be documented. No revision to the SAP is required for changes which do not affect the statistical analysis methods, definitions, or rules defined in this document. If additional analyses are required to supplement the planned analyses described in the SAP, the changes and justification for the changes will be outlined in the associated clinical study report (CSR). No change will be made without prior approval of the Sponsor.

When applicable, all methodologies and related processes will be conducted according to Syneos Health Standard Operating Procedures (SOPs) as appropriate. Shells for all statistical tables, listings, and figures referred to in this SAP will be displayed in a separate document.

1.1 Responsibilities

Syneos Health will perform the statistical analyses and are responsible for the production and quality control of all safety, PK, immunogenicity and PD analysis and tables, listings, figures (TLFs).

1.2 Timings of Analyses

Interim Analysis:

Interim analysis of safety and PK will be performed for each dose level using available blinded serum concentrations data (up to 48 hours post-start infusion) will be reviewed at Safety Review Committee (SRC) meeting prior to dose escalation.

Final Analysis:

The final analyses of safety, PK, immunogenicity, and PD will be completed after subjects complete the final study visit or terminate early from the study.

This document is confidential.

2. Study Objectives

- Primary objectives:
 - To assess the safety and tolerability of NS101 following intravenous (IV) administration of single ascending doses in healthy subjects
- Secondary objectives:
 - To characterize the PK profile of NS101 in serum and NS101 concentrations in cerebrospinal fluid (CSF) following single IV infusion doses in healthy subjects.
 - To characterize the PD profile of NS101 through FAM19A5 in plasma and FAM19A5 concentrations in CSF following single IV infusion doses in healthy subjects.
 - To evaluate the immunogenicity profile of NS101.

This document is confidential.

3. Study Description

This study is a single center Phase I, first-in-human (FIH), single ascending dose (SAD), double bind study to evaluate the safety, tolerability, PK, PD, and immunogenicity of NS101 in healthy volunteers and aid in the selection of optimal doses and dosing regimens for future studies. The study consists of up to 8 cohorts. The cohorts will be dosed sequentially.

3.1 Subject Selection

Up to 80 healthy, non-smoking, male volunteers aged 18 to 55 years, with body mass index (BMI) >18.5 and $<30.0 \text{ kg/m}^2$ and body weight $\geq 50.0 \text{ kg}$, will be enrolled in this study.

3.2 Determination of Sample Size

The sample size of this study is not determined based on statistical calculations, it is rather determined based on the probability of observing an adverse event (AE). A sample size of 8 subjects per cohort randomized in a 3:1 ratio to the study drug versus placebo represents a typical panel for a FIH study. This number of subjects is judged adequate to achieve the study objectives.

3.3 Treatment Assignment

All subjects enrolled will receive a single infusion of NS101, or matching placebo, under fasting conditions over a period of approximately 1 hour, at the target dose levels listed in the table below. Each subject's body weight on Day -1 will be used to calculate the dose required, based on their assigned dose level [body weight (kg) x dose level (mg) = administered dose (mg)].

Cohort Number	Dose level	Number of subjects receiving NS101	Number of subjects receiving placebo
1	0.25 mg/kg	6 (1 sentinel, 5 non-sentinel)	2 (1 sentinel, 1 non-sentinel)
2	0.75 mg/kg	6 (1 sentinel, 5 non-sentinel)	2 (1 sentinel, 1 non-sentinel)
3	1.50 mg/kg	6 (1 sentinel, 5 non-sentinel)	2 (1 sentinel, 1 non-sentinel)
4	3.0 mg/kg	6 (1 sentinel, 5 non-sentinel)	2 (1 sentinel, 1 non-sentinel)
5	6.0 mg/kg	6 (1 sentinel, 5 non-sentinel)	2 (1 sentinel, 1 non-sentinel)
6	12.0 mg/kg	6 (1 sentinel, 5 non-sentinel)	2 (1 sentinel, 1 non-sentinel)
7	24.0 mg/kg	6 (1 sentinel, 5 non-sentinel)	2 (1 sentinel, 1 non-sentinel)
8	48.0 mg/kg	6 (1 sentinel, 5 non-sentinel)	2 (1 sentinel, 1 non-sentinel)

Note: Adjustments to the currently outlined dose levels may be made based on data from completed dose levels. However, the dose to be administered in a given cohort will not exceed the one currently outlined in the protocol.

3.4 Randomization

Randomization schedules will be generated through SAS® for Windows, Release 9.4 (SAS Institute Inc., Cary, NC, USA) software, prior to study execution. Block randomization will be used, and one randomization scheme will be produced for each cohort separately.

Subjects eligible for participation will be randomized (on Day 1) to receive NS101 or placebo in a 3:1 ratio, for a total of 6 subjects receiving NS101 ("active") and 2 subjects receiving matching placebo in each dose level. Each cohort will include 2 sentinel subjects randomized in a 1:1 ratio (1 active and 1 placebo) dosed initially, and the remaining 6 subjects (5 active and 1 placebo) will be dosed at least 48 hours later (each dosed at least 15 minutes apart).

This document is confidential.

Subjects assigned to Cohorts 5 through 8 will be randomized a second time for collection of a CSF sample at one of the following timepoints: 24, 36, 168, or 336 hours post-start of infusion. Each of the 4 timepoints will be assigned to 2 subjects. Sentinel subjects will be randomized to the same timepoint, to ensure that each timepoint is assigned to at least 1 subject receiving the active drug, NS101.

Due to the limited availability of the anesthesiologist performing the procedure, the assignment of timepoints for CSF collection, initially only determined by the randomization scheme, may be modified in consideration of each subject's dosing date and time. For example, 2 subjects allocated to one CSF timepoint may swap their timepoint with that of 2 subjects assigned to another timepoint. Importantly, although the attribution of timepoints will differ from the initial randomization scheme, the overall requirements outlined in the protocol in terms of number of subjects per timepoint (2 subjects), and assignment of sentinel subjects to the same timepoint, will be respected.

3.5 Blinding:

The subjects and the clinical personnel involved in the collection, monitoring, revision, or evaluation of AEs, or personnel who could have an impact on the outcome of the study will be blinded with respect to the subject's treatment assignment (NS101 or placebo). Blinding will be maintained until the database is locked and the analysis population are determined.

The randomization schedule for cohort 1 to 8 was provided according to randomization specification. Designated pharmacy personnel at the clinical site not directly involved with the clinical aspects of the trial will prepare and dispense the study medication and will be aware of the randomization code. The study drug and placebo will have the same visual appearance in order to avoid compromising the study blinding.

In the event of an emergency for an individual subject in which knowledge of the study treatment is critical to the subject's medical management or for the decision of dose escalation, the Investigator may break the blind for that subject. An envelope for each subject containing the treatment assignment will be available from the pharmacy personnel. The Investigator or other attending study physician will make every effort to contact the Sponsor prior to unblinding a subject's treatment assignment and will record the date and reason for unblinding in the study source documents.

As all samples (including placebos) will be analyzed, the randomization code will not be available to the Bioanalytical Division of Syneos Health prior to analysis from each cohort. However, since concentrations of NS101 above the analytical method's lower limit of quantification (LLOQ) should not be observed for subjects receiving the placebo, blinding of treatment assignments by personnel in the Bioanalytical Division involved with sample analysis cannot be assured completely.

Blinded PK results will be available during the course of the study. These results will be reported without revealing the subject's identity.

3.6 Subject Withdrawal and Replacement

Subjects who withdraw, or are withdrawn, from the study for safety and tolerability reasons after

This document is confidential.

dosing will not be replaced. However, subjects who withdraw or are withdrawn from the study after dosing for reasons other than safety and tolerability, may be replaced. The total number of subjects dosed (including potential replacement subjects) will remain within a maximum of 10 subjects per cohort.

This document is confidential.

4. Endpoints

- Primary endpoints:
 - Incidence, nature, relatedness, and severity of AEs.
 - Changes in vital signs measurements, physical examination, clinical laboratory test findings, and 12-lead electrocardiogram (ECG) results.
- Secondary endpoints:
 - Serum PK parameters for NS101 will include the following:
 - area under the concentration-time curve, from time zero to 24-hours (AUC_{0-24})
 - area under the concentration-time curve from time zero until the last observed concentration (AUC_{0-t})
 - area under the concentration-time curve from time zero to infinity ($AUC_{0-\infty}$)
 - maximum observed concentration (C_{max})
 - time when the maximum concentration is observed (T_{max})
 - terminal elimination half-life ($T_{1/2 el}$)
 - elimination rate constant (K_{el})
 - apparent body clearance (Cl)
 - apparent volume of distribution (V_z)
 - Concentrations of NS101 in CSF for Cohorts 5 to 8
 - Serum to CSF ratio of NS101 concentrations
 - Immunogenicity of NS101, measured as the number and percentage of subjects who develop detectable anti-drug antibody (ADA) and neutralizing antibody (NAb)
- Exploratory endpoints:
 - Effect (E): variation of level of FAM19A5 ($\Delta FAM19A5$) following administration of NS101:
 - PD: Change in baseline of FAM19A5 levels
 - The following PD parameters in plasma:
 - $AUEC_{0-t}$
 - maximal observed effect (E_{max})
 - time of maximal observed effect (TE_{max})
 - Concentrations of FAM19A5 in CSF

This document is confidential.

5. Analysis Populations

All subjects' inclusion status into each analysis population will be determined after database lock.

5.1 Randomized Population

The randomized population is defined as all subjects who were randomized.

5.2 Safety Population

The safety population is defined as all subjects who received any amount of NS101 or placebo.

5.3 PK Concentration Population

The PK concentration population will include all subjects who received NS101 and have at least one post-dose concentration \geq LLOQ.

5.4 PK Parameter Population

The PK parameter population will comprise all subjects who received any amount of NS101 and have sufficient post-dose serum concentration-time data to adequately determine at least one PK parameter. Any subject who has at least one major protocol deviation which might have an impact on the PK parameter analyses will be excluded from the PK population.

Here are some aspects to be considered (but not to be limited to) when determining data availability for the PK population: inclusion and exclusion criteria, acceptable times for visit dates and measurements, compliance with treatment, the nature and quality of the data, withdrawal, and any protocol deviation. The final responsibility of deciding which subjects are to be included or excluded lies with the PI and/or the sponsor.

5.5 CSF Population

The CSF population is defined as all subjects having received at least one dose of NS101 and CSF sample collected.

5.6 PD Population

The PD population will include all subjects having received at least one dose of NS101, as appropriate, and for whom at least one post-dose FAM19A5 parameter can be adequately characterized.

5.7 Immunogenicity Population

The immunogenicity population will include all subjects who have received any amount of NS101 and have at least one post-dose ADA/NAb measurement.

This document is confidential.

6. General Aspects for Statistical Analysis

6.1 General Methods

SAS for Windows, Release 9.4, software will be used to perform all data analyses.

All data in the database will be presented in the data listings. Unless otherwise stated, all listings will be sorted by randomized cohort, subject number, and assessment date and time. For the purposes of the summary tables, all subjects randomized to placebo will be pooled into a single placebo group.

The following labels for treatment will be used on all tabulations where the results are displayed by treatment, in the following order:

- All Placebo
- NS101 0.25 mg/kg
- NS101 0.75 mg/kg
- NS101 1.50 mg/kg
- NS101 3.0 mg/kg
- NS101 6.0 mg/kg
- NS101 12.0 mg/kg
- NS101 24.0 mg/kg
- NS101 48.0 mg/kg

6.2 Summary Statistics:

Unless otherwise stated, continuous variables will be summarized using the number of observations (n), and the statistics mean, median, standard deviation (SD), minimum (min) and maximum (max). The min and max values will be presented to the same number of decimal places as recorded in the case report form (CRF), median will be presented to one more decimal place than the raw data and the mean and SD will be presented to two more decimal places than the raw data. Summaries of change-from-baseline variables will include only subjects who have both a baseline value and corresponding value at the timepoint of interest. Categorical variables will be summarized with frequency counts and percentages. Percentages will be rounded to one decimal place, with the denominator being the number of subjects in the relevant population, unless otherwise stated.

For the serum and CSF PK and PD data, the data will be rounded to two decimal places in the listings, except for the following situations:

- Elimination rate constant (K_{el}) data: rounded off to four decimal digits
- PK parameters related to time, such as T_{max} , $K_{el\ Lower}$, and $K_{el\ Upper}$, will be reported with the same precision as the actual sampling time: rounded off to 3 decimal digits
- Concentration versus time data, as well as C_{max} : reported as they appear in the corresponding dataset

Summary statistics include the geometric mean (two decimal places) and coefficient of variation (CV)% (two decimal place). The geometric mean and CV% will not be calculated for T_{max} , $T_{1/2\ el}$, and K_{el} .

This document is confidential.

Only data from protocol scheduled (“nominal”) visits / timepoints will be included in the summary tables. Data from unscheduled visits will not be included in the summary tables (unless they were used as baseline) but will be included in the listings.

In the case of a repeat test, both assessments will be presented in the listings. If a repeat measurement was performed due to the first measurement being outside the normal range for the given assessment and the second assessment confirms the first measurement, then only the first measurement will be used for analysis and the second assessment will be considered an unscheduled timepoint. In the same case, if the second assessment falls within normal ranges, then the second assessment will be used for analysis of that timepoint. In all other cases, the first measurement will be taken as the assessment to be used for the analysis.

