5.4.1 Anticipated Clinical Risks and Benefits

Healthy subjects will not benefit from this study. However, the data from this study may be potentially helpful for future subjects with AD, ALS, or SCI.

Anticipated clinical risks include the following:

• The human-equivalent doses of the two concentrations (10 ug/mL and 100 ug/mL) at which cytokine release may be expected (section 5.2.6) were calculated and found to be 0.375 ~ 3.75 mg/kg in adult males. NS101 in comparison to cetuximab showed slightly higher level of IL-8, and TNF-α; however, the extent of this level was statistically insignificant. For this FIH study, the maximum selected dose is 12 mg/kg, and, from this dose, the expected C_{max} should be approximately 31 ug/mL. Some level of cytokine release may be expected due to the expected C_{max} concentration. With reference to the cytokine profile of NS101 from previous study, we may predict slightly higher level of cytokine release than that of cetuximab.

Accordingly, infusion-related reactions will be carefully monitored throughout the study.

 Acute reactions following infusion of monoclonal antibodies can be caused by various mechanisms, including acute anaphylactic (IgE-mediated) reactions, serum sickness, tumor lysis syndrome (TLS) and cytokine release syndrome (CRS). Clinical manifestations may include local skin reactions at the injection site, pyrexia and an influenza-like syndrome, to acute anaphylaxis and systemic inflammatory response syndrome. Infusion reactions may occur after NS101 administration.

This can be managed by recognition of risk factors, appropriate monitoring and prompt intervention. Appropriate hydration and diuresis, premedication and cautious incremental increases in the rate of infusion can minimize risk.

• Lumbar puncture, planned for the current study, may cause headache due to leakage of fluid, pain, bleeding, and brainstem herniation. Subjects will remain at the clinic for a sufficient period of time after the procedure for adequate monitoring.

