5.4.2 PK and PD Parameters

NS101 concentrations will be measured in serum for PK evaluation. As PK-PD relationship between NS101 and FAM19A5 has been demonstrated in preclinical studies, FAM19A5 in plasma has been selected as a PD marker for the current study. Furthermore, as presence of NS101 and FAM19A5 has been observed in CSF and is essential for drug efficacy, both NS101 and FAM19A5 will be also measured in CSF after collection via lumbar puncture. In order to mitigate risks associated with lumbar puncture, each subject will be randomized to a single timepoint at which they will undergo lumbar puncture. Furthermore, as lower dose levels that were selected for this study are expected to exhibit no to minimal pharmacological activity, CSF samples will be only collected starting from the medium to high dose levels (Cohorts 5 to 8) of the current study. NS101 and FAM19A5 in CSF samples from subjects who will be administered the placebo treatment will be used as baseline.

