11.8.3 Lumbar Puncture for CSF Sampling

For Cohorts 5 to 8 only: for each subject, a single CSF sample will be collected via lumbar puncture for PK and PD analysis. The volume of collected CSF per sample should not exceed approximately 6 mL.

Subjects in each cohort will be randomized to have their CSF sample collected at one of the following timepoints, so as to have 2 subjects assigned to each timepoint: 24 (±3 hours; Day 2), 36 (±3 hours; Day 2), 168 (Day 8±1), or 336 (Day 15±1) hours post-start of infusion, according to

the randomization scheme. Sentinel subjects will be randomized to the same timepoint. Placebo subjects will serve to evaluate change from baseline.

Lumbar puncture may require administration of a local anesthetic, such as lidocaine. Details would be described in a separate document.

A catheter will be inserted during the procedure for safety.

Following the lumbar puncture, subjects could be observed for up to 6 hours while in supine position. The Investigator or designee will then assess the subject to determine whether it is safe for them to leave the clinic. If there is a safety concern, the Investigator or designee can request the subject to remain for further monitoring as needed. Subjects should refrain from physically strenuous activities for 12 hours after lumbar puncture and may then resume their usual routines.

Vital signs will be also measured before lumbar puncture and will be measured approximately 0.5 hours after lumbar puncture, meaning approximately 24.5 (±3 hours; Day 2), 36.5 (±3 hours; Day 2), 168.5 (Day 8±1), or 336.5 (Day 15±1) hours post-start of infusion, according to the randomization scheme.

PO will be performed during lumbar puncture: 24 (±3 hours; Day 2), 36 (±3 hours; Day 2), 168 (Day 8±1), or 336 (Day 15±1) hours post-start of infusion, according to the randomization scheme.

Details will be included in the PSP.

Cumulative safety/tolerability data from early cohorts will inform on whether lumbar puncture will be started at Cohort 5.

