11.14.4 Assessment of Relationship to Study Drug

Each AE must be classified based on medical judgment and according to the following relationship categories: probable, possible, remote/unlikely, and unrelated. The definitions for the relationship categories are as follows (Table 15):

Table 15. Description of Adverse Event Relationship Categories

Category	Description
	This category applies to AEs that are considered, with a high degree of certainty, to be related to the investigational product. An AE may be considered probable, if:
	1. It follows a reasonable temporal sequence from the administration of the drug.
Probable	2. It cannot be reasonably explained by the known characteristics of the participant's clinical state, environmental or toxic factors or other modes of therapy administered to the participant.
	3. It disappears or decreases on cessation or reduction in dose (there are important exceptions when an AE does not disappear upon discontinuation of the drug, yet drug relatedness clearly exists; e.g. (1) bone marrow depression, (2) tardive dyskinesias).
	4. It follows a known pattern of response to the suspected drug.
	5. It reappears upon re-challenge. [Related] Possible (must have first two points)
	This category applies to AEs in which the connection with the investigational product administration appears unlikely but cannot be ruled out with certainty. An AE may be considered possible if, or when:
Possible	1. It follows a reasonable temporal sequence from the administration of the drug.
	2. It may have been produced by the participant's clinical state, environmental or toxic factors, or other modes of therapy administered to the participant.
	3. It follows a known pattern of response to the suspected drug.

Category	Description
	In general, this category is applicable to an AE that meets the following criteria:
	1. It does not follow a reasonable temporal sequence from the administration of the investigational product.
Remote/Unlikely	2. It may readily have been produced by the participant's clinical state, environmental or toxic factors, or other modes of therapy administered to the participant.
	3. It does not follow a known pattern of response to the suspected drug.
	4. It does not reappear or worsen when the investigational is readministered.

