Unrelated	This category is applicable to AEs that are judged to be clearly and incontrovertibly due only to extraneous causes (disease, environment, etc.), and do not meet the criteria for medication relationship listed under remote, possible, or probable.

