8.4 CSF PK Sampling Schedule

Subjects included in Cohorts 5 through 8 will have one CSF sample collected, via lumbar puncture, at one of the following timepoints: 24, 36, 168, or 336 hours post-start of infusion.

NS101 concentrations in CSF will be presented in the listings, as well as the ratio of NS101 in serum to NS101 in CSF at the applicable time-matched timepoint, i.e. serum NS101/CSF NS101 at time xx hrs.

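### The single pooled placebo column in the TEAE tables mixes lumbar-puncture and non-puncture cohorts half and half, so no dose column has a like-for-like placebo column for puncture-type events

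*SAP*

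**What the plan says.** SAP 6.1 sets the placebo rule: "For the purposes of the summary tables, all subjects randomized to placebo will be pooled into a single placebo group". The same section fixes the labels for every tabulation by treatment as All Placebo followed by the eight dose levels. SAP 11.2 tabulates TEAEs by treatment and lists six summaries: overall; SOC and PT; severity; relationship; serious; and those above 5% overall. None is by placebo cohort or by puncture.

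On the procedure, Protocol 5.4.2 says "CSF samples will be only collected starting from the medium to high dose levels (Cohorts 5 to 8) of the current study", and SAP 8.4 says "Subjects included in Cohorts 5 through 8 will have one CSF sample collected, via lumbar puncture". This includes placebo subjects, whose CSF values serve as the baseline (Protocol 5.4.2). The start is conditional: "Cumulative safety/tolerability data from early cohorts will inform on whether lumbar puncture will be started at Cohort 5" (Protocol 11.8.3). Protocol 5.4.1 names the expected harms: "Lumbar puncture, planned for the current study, may cause headache due to leakage of fluid, pain, bleeding, and brainstem herniation".

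On attribution, Protocol 11.14.4 says "Each AE must be classified based on medical judgment and according to the following relationship categories: probable, possible, remote/unlikely, and unrelated". All four categories refer to the study drug; none refers to the procedure.

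On listings, SAP 6.1 says "Unless otherwise stated, all listings will be sorted by randomized cohort, subject number, and assessment date and time", while SAP 14.1.5.3 orders listings by treatment group first.

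**The concern.** Puncture takes place 24 to 336 hours after the start of infusion. SAP 11.2 counts as treatment-emergent any AE that begins at or after dosing, so events caused by the puncture enter the TEAE tables. AE incidence is a primary endpoint and is read descriptively, by comparing each dose column with placebo.

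For puncture-type events that comparison is uneven. Every subject at 6 to 48 mg/kg is due a puncture, nobody at 0.25 to 3 mg/kg is, and half of the placebo column is. With no drug effect at all, the upper four dose columns would tend to lie above placebo and the lower four below it. Because the shift has the same sign in all four columns on each side, reading across doses does not average it out. The placebo subjects who could show whether the same rise occurs without drug, those in Cohorts 5 to 8, are not visible as a group in any summary that the SAP describes.

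**Working it through.** **Counts.** Inputs: 8 cohorts, each with 6 NS101 and 2 placebo subjects (SAP 3.3); puncture in Cohorts 5 to 8 (Protocol 5.4.2, SAP 8.4).

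- Total: 8 × (6 + 2) = 64, which reproduces the figure in Protocol 10.1.
- All Placebo: 8 × 2 = 16, of whom 4 × 2 = 8 (50%) are in puncture cohorts.
- NS101 6 to 48 mg/kg: 4 × 6 = 24, of whom 24 (100%) are.
- NS101 0.25 to 3 mg/kg: 4 × 6 = 24, of whom 0 are.

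These are planned numbers; replacements (up to 10 dosed per cohort) could change them. If puncture started at Cohort 6, the counts would be 6 of 16 on placebo and 18 of 24 at 6 to 48 mg/kg.

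**Size of the mismatch.** The documents give no AE rate for puncture, so the rates here are assumptions. Let b be the background risk and q the puncture risk, with no drug effect. Then p = 1 − (1 − b)(1 − q) is the risk in a punctured group, (b + p)/2 the pooled placebo risk, and (p − b)/2 the shift each way. The standard error (SE) of a 6-subject column is √(p(1 − p)/6) with puncture and √(b(1 − b)/6) without. With b = 10%:

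| q | p | All Placebo | Shift (points) | SE, punctured | SE, unpunctured |
|---|---|---|---|---|---|
| 10% | 19% | 14.5% | 4.5 | 16.0 | 12.2 |
| 20% | 28% | 19% | 9 | 18.3 | 12.2 |
| 30% | 37% | 23.5% | 13.5 | 19.7 | 12.2 |
| 40% | 46% | 28% | 18 | 20.3 | 12.2 |

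The shift stays below the SE of a punctured column throughout. It passes that of an unpunctured column at about q = 27%, because the shift is 0.9q/2 and 2 × 12.2/0.9 ≈ 27. With b varied from 2% to 20%, the shift runs from 4.0 points (b = 20%, q = 10%) to 19.6 points (b = 2%, q = 40%).

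**What a split would show.** Expected placebo subjects with an event are 8b = 0.8 of 8 in Cohorts 1 to 4, and 8p = 1.5, 2.2, 3.0 and 3.7 of 8 in Cohorts 5 to 8. The pooled column shows only their sum: 2.3, 3.0, 3.8 and 4.5 of 16. The probability that the Cohorts 5 to 8 count exceeds the Cohorts 1 to 4 count, P(Bin(8, p) > Bin(8, b)), is 56, 73, 85 and 93%. The reference value with no puncture effect is (1 − P(tie))/2 = (1 − 0.355)/2 = 32%. At b = 20% the range is 53 to 87%, against 37%.

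**What a split would not do.** Take the root mean square error of dose minus placebo, true difference zero, at b = 10%. Pooled is √(shift² + p(1 − p)/6 + V) with V = [8b(1 − b) + 8p(1 − p)]/256. Split is √(p(1 − p)/6 + p(1 − p)/8). For an unpunctured column, replace p by b in the dose and split terms.

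| q | Punctured: pooled | Punctured: split | Unpunctured: pooled | Unpunctured: split |
|---|---|---|---|---|
| 10% | 18.8 | 21.2 | 15.7 | 16.2 |
| 20% | 22.5 | 24.2 | 17.9 | 16.2 |
| 30% | 25.9 | 26.1 | 20.8 | 16.2 |
| 40% | 29.0 | 26.9 | 24.1 | 16.2 |

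Against one punctured dose column, the pooled comparator has the smaller error up to 30% risk. Against an unpunctured column, the split is better from 20%. Exact (Clopper-Pearson) 95% intervals show how little 8 subjects say: 0 of 8 gives 0 to 37%, and 2 of 8 gives 3 to 65%.

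**The case against.** The strongest reply is that nothing here is an error. The pooling rule is stated openly and agrees with SAP 11.2, SAP 11 plans no inferential safety analysis, and the Safety Review Committee works cohort by cohort and cumulatively (Protocol 9.1). This stands, and it limits the point to presentation.

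A reader might infer that pooling creates the step between 3 and 6 mg/kg. It does not: the step comes from confining puncture to Cohorts 5 to 8 and would remain in the dose columns under any placebo layout. The split only shows whether placebo has the same step.

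A reader might also infer that the split columns should replace All Placebo. The error figures do not support that for the punctured columns, where pooling is mostly the more precise choice. At 10% puncture risk the split is also weakly informative: 56% against the 32% expected with no effect.

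The plan offers partial remedies. The relationship table can move procedural events out of the drug-related rows: for the unrelated category the protocol says "This category is applicable to AEs that are judged to be clearly and incontrovertibly due only to extraneous causes", and remote/unlikely can take others. But the possible category also admits events that other factors may have produced, so the separation is incomplete. All AEs are listed, so a reader could rebuild the split by hand. However, SAP 6.1 and SAP 14.1.5.3 disagree on listing order, and a primary-endpoint table should not need such work. Subject numbers seem to carry the cohort (SAP 11.4 gives 4001 to 4005 for Cohort 4), which would help. The table shells are a separate document and could not be checked.

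**Conclusion.** The point holds as a minor one. The documents establish the imbalance of 8 of 16 against 24 of 24 and 0 of 24, the protocol's own expectation of puncture-related events, and the absence of any TEAE summary in the SAP that separates them. The 4.5 to 18 point shift is not established by the documents; it follows from an assumed 10% background, an assumed 10 to 40% puncture risk and no drug effect. Even then it is generally no larger than the sampling error of one 6-subject column, except for unpunctured columns at the higher assumed risks.

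A reader might conclude that escalation decisions or the safety conclusions are compromised. The documents do not support this: no test or escalation rule uses the pooled column. What is affected is how the final TEAE tables read for headache, pain, bleeding and similar events.

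**What to change.** Keep All Placebo. In the TEAE tables by SOC and PT, add two supplementary placebo columns defined by cohort: cohorts without lumbar puncture (planned Cohorts 1 to 4, n=8) and cohorts with it (planned Cohorts 5 to 8, n=8). If puncture starts later, place the boundary at the cohort where it actually starts; a start at Cohort 6 would give 10 and 6. Define the columns by cohort, which is the unit of randomization, and not by whether each subject was in fact punctured. State in the SAP that the split columns are for reading puncture-type events only, do not replace the pooled column, and at n=8 cannot confirm or exclude a drug effect. Reconcile the listing order in SAP 6.1 and SAP 14.1.5.3.

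A listing flag for AEs with onset after puncture is optional. SAP 11.2 foresees missing onset dates and times, and the actual times in Protocol 11.8.5 concern samples, so the flag should apply only where the onset allows and read as unknown otherwise.

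The cost is SAP wording and two columns, with no new data for the split. The downside is two imprecise extra columns that a reader could over-interpret.
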